## General objective

Demonstrate that frequency spectroscopic analysis of raw ultrasound (RF) data enables the detection, classification, and differentiation of different tissue-specific entities.

## Initial more specific hypotheses:

1. The evaluation of RF data of the liver by neural networks with liver elastography results as a reference standard enables the detection and classification of degrees of steatosis, fibrosis and cirrhosis.
2. Neural networks trained on RF data are better than networks trained on B-scans at detecting degrees of steatosis, fibrosis, and cirrhosis as measured in AUC.
3. The diagnostic certainty of the degree of steatosis, fibrosis and cirrhosis of a neural network trained on RF data depends on the bandwidth of the US signal provided
4. The evaluation of RF data of the liver by neural networks with histology results as a reference standard enables the detection and classification of hepatic cavities.
5. The evaluation of RF data of the liver by neural networks with results of contrast ultrasonography as a reference standard enables the detection and classification of hepatic cavities.
6. Neural networks trained on RF data are better than networks trained on B-scans in classifying liver cavities.

## 3. Study design

The study is designed as a prospective, multicenter, experimental study. Female and male patients undergoing sonographic examination with biopsy, CEUS or elastography will be included. It is important to ensure that the corresponding examinations would also be carried out independently of the study so as not to create any additional effort for the patient. The only difference is the additional systemic acquisition of raw ultrasound data, which is not always stored in conventional examinations.

## Type of study

- prospective, multicenter, experimental study

## Sample size planning

For the validation of the networks, a sample size of at least 200 patients is targeted. After completion of the data collection, each degree of fibrosis should be present about 20 times in order to enable a valid performance of the network for each degree of fibrosis. If this is not achieved, data collection will continue for 100 additional patients and then the distribution will be reviewed again. This is repeated until the target minimum number is reached. For focal

lesions we plan to include 50 patients per lesion. If this criterion is not met, data acquisition continuous.

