### Goal

Within the framework of basic research, multicenter *prospective*, anonymized, broadband raw ultrasound data are to be collected for the first time in a common database. The basis for this database is the cooperation of several German centers (previously planned: University Hospital Dresden, Municipal Hospital Dresden, University Hospital Leipzig, University Hospital Halle). These data will be used to evaluate a trained neural network, which can classify liver fibrosis based on RF data.

To collect the necessary amounts of data, further centers are to be included in the course of the process. Thus, the study builds on previous analyses from *retrospective* data from the University Hospital Dresden (ethics application BO-EK-534122022) and is intended to test some of the promising preliminary results in a prospective approach.

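### Does the enrolment rule need a precision basis for 20 patients per fibrosis degree, and a matching count for the AUC comparison and for steatosis?

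*Protocol*

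**What the plan says.** **Protocol, section 3, Sample size planning.** The minimum total comes first: "For the validation of the networks, a sample size of at least 200 patients is targeted". A count per stage is then required at the end of recruitment: "each degree of fibrosis should be present about 20 times in order to enable a valid performance of the network for each degree". The section goes on to say what happens when a stage falls short: "If this is not achieved, data collection will continue for 100 additional patients and then the distribution will be reviewed again". The stopping point of these extensions is given as follows: "This is repeated until the target minimum number is reached". A separate criterion asks for 50 patients per focal lesion. Steatosis is not mentioned, and no accuracy measure, interval width, significance level or power is given.

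**Protocol, section 2, Initial more specific hypotheses.** Hypothesis 1, which takes elastography as its reference, claims that the RF evaluation "enables the detection and classification of degrees of steatosis, fibrosis and cirrhosis". Hypothesis 2 claims that RF networks perform "better than networks trained on B-scans at detecting degrees of steatosis, fibrosis, and cirrhosis as measured in AUC". Hypothesis 3 concerns signal bandwidth: "The diagnostic certainty of the degree of steatosis, fibrosis and cirrhosis of a neural network trained on RF data depends on the bandwidth".

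**Protocol, section 1, Goal.** The work is described as basic research, and its use is stated for fibrosis: "These data will be used to evaluate a trained neural network, which can classify liver fibrosis based on RF data".

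**The concern.** The Protocol itself fixes when enrolment ends, so patients not recruited under this rule cannot be recovered at analysis. Three things look wrong.

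- The number 20 is justified only by a general appeal to valid performance, with no precision behind it.
- Hypothesis 2 is a superiority claim about AUC, but neither 200 nor 20 is related to a difference in AUC. If the comparison were made at the rarest degree, the interval could be too wide to separate RF from B-scan networks.
- Hypotheses 1 to 3 cover steatosis degrees, but the review that decides on extension counts fibrosis degrees only. Enrolment could end with very few patients in a steatosis degree.

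At stake would be an uninformative answer to hypothesis 2 and weak evidence on steatosis.

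**Working it through.** **1. Can the Protocol's figures be reproduced?** The inputs given are a total of at least 200, about 20 per fibrosis degree, extension by 100, and 50 per focal lesion. No significance level, power, expected AUC, difference or interval width is stated. So neither 200 nor 20 can be derived, and neither can be shown to fall short of a stated aim. All AUCs, correlations, splits and prevalences below are assumptions.

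**2. One AUC, one degree against the rest, at the floor (m = 20, n = 180).** Hanley-McNeil: SE² = [A(1−A) + (m−1)(Q₁−A²) + (n−1)(Q₂−A²)] / (mn), with Q₁ = A/(2−A) and Q₂ = 2A²/(1+A).

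- A = 0.80: (0.160 + 0.507 + 12.729)/3600 = 0.003721; SE 0.0610; half-width 1.96 × 0.0610 = 0.120.
- A = 0.90: (0.090 + 0.156 + 7.631)/3600 = 0.002188; SE 0.0468; half-width 0.092.

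Simulation of the same AUC with equal-variance binormal scores (20,000 runs) gives about 0.100 and 0.070. The formula is wider by 0.120/0.100 = 1.20 and 0.092/0.070 = 1.31. Any figure written into the Protocol would therefore depend on the method by some 20 to 30%.

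**3. Difference between two AUCs on the same patients.** Half-width = 1.96 × √(SE₁² + SE₂² − 2r·SE₁·SE₂), with r the correlation between the two AUC estimates.

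| Split | AUCs | r = 0.3 | r = 0.5 | r = 0.7 |
|---|---|---|---|---|
| 20 vs 180 | 0.80, 0.80 | 0.141 | 0.120 | 0.093 |
| 20 vs 180 | 0.80, 0.85 | 0.135 | 0.114 | 0.089 |
| 20 vs 180 | 0.90, 0.90 | 0.108 | 0.092 | 0.071 |
| 80 vs 120 | 0.80, 0.80 | 0.078 | 0.066 | 0.051 |
| 80 vs 120 | 0.80, 0.85 | 0.073 | 0.062 | 0.048 |
| 80 vs 120 | 0.90, 0.90 | 0.057 | 0.048 | 0.037 |

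The wide intervals belong to the 20 vs 180 split. Hypothesis 2 speaks of detecting degrees by AUC. It does not claim superiority separately at each degree, so that split is a reading brought to the text. At a middle cut-off the same 200 patients give about half the width, but the 80 vs 120 split is itself assumed, because the Protocol gives no distribution of degrees.

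**4. Would naming a middle cut-off settle hypothesis 2?** Not by itself. With an even 100 vs 100 split and r from 0.3 to 0.7, power at the two-sided 5% level is 30 to 58% for 0.80 vs 0.85 and 86 to 99% for 0.80 vs 0.90. The answer turns on the true difference, for which the Protocol gives no value.

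**5. Does 20 of 200 describe the sample?** Only if every patient has a fibrosis degree. Sections 3 and 4 admit patients having biopsy, CEUS or elastography, and a patient with a focal lesion seen on CEUS need not be staged. The lesion criterion can also take the total beyond 200.

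**6. Steatosis.** The chance that a steatosis degree reaches 20 among 200 patients is binomial: 0.3% at an assumed prevalence of 5%, 53% at 10%, and 98.5% at 15%. If the fibrosis number were applied to steatosis as well, starting from 200 and adding blocks of 100, mean enrolment would be about 450, 300, 248 or 201 at prevalence 5%, 8%, 10% or 15%. These totals ignore extensions that the fibrosis count may already have triggered.

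**The case for a change.** The strongest case for a change is that this is an enrolment rule and not an analysis detail. A later analysis plan cannot restore patients who were never recruited, the Protocol offers a reason for 20 that it does not back, and hypothesis 2 is worded as superiority. Rewording would cost no patients, and fixing one cut-off before the networks are run on the prospective data would make hypothesis 2 easier to answer.

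Part of this stands. The text is as described, the rationale for 20 is thin, and steatosis has no number per degree. The rest does not carry a change:

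- The minimum of 200 applies to validation in general, so steatosis has a sample size, though not one per degree.
- A cut-off can still be named in the analysis plan before the networks are run, so nothing is lost by its absence here.
- An AUC half-width in the sample size section would depend on the method and might not describe the staged sample.
- Calling steatosis exploratory would alter no count and no estimate, and the hypotheses are already presented as initial. Counting its degrees would add patients for a use that the Goal section does not name.

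**Conclusion.** No change follows. The Protocol sets a workable recruitment rule for its stated purpose, the evaluation of a fibrosis classifier, and the rule and the goal agree. What is missing is a rationale for 20 and an analysis specification for hypothesis 2. The first contradicts no target in the document, and the second is ordinary content of an analysis plan. At the floor, a single AUC carries a half-width of about 0.07 to 0.12, according to the method and to an assumed AUC of 0.80 or 0.90. That is coarse, but it will be visible in the reported intervals. The steatosis mismatch is real and small: results for a rare steatosis degree may rest on few patients, and analysts can report them with their counts and intervals. The conclusion rests on fibrosis being the main use of the data, as the Goal section says. It would need another look if the sponsor meant hypotheses 1 to 3 to be confirmed for each steatosis degree, which nothing in the Protocol states.

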#### 4. Test Method

##### Study population

Female and male subjects over 18 years of age who are undergoing biopsy, CEUS, or elastography as part of an ultrasound scan.

##### Inclusion Criteria

- Age over 18 years
- Subject's capacity to give consent
- Signed declaration of consent by the subject

##### Exclusion criteria

- minor intervention (e.g. biopsy) performed less than a week ago in the same area
- CEUS carried out less than a day ago
- Major intervention on the liver (e.g. resection) in the history

##### Course of study

The required RF data is recorded shortly before the actual investigations, which provide us with the required ground truth. The data acquisition is carried out with approved devices from everyday clinical use. Specifically, Clarius' C3HD3 US handheld models are used as a low-frequency abdominal transducer and Clarius' L15HD3 as a high-frequency linear transducer. The data from the two transducers are combined in the evaluation to simulate broadband recordings. In the so-called RF mode, both B-scans and ultrasonic raw data are recorded in the form of RF data. The raw data is only recorded within a predefined region of interest (ROI).

The data is then temporarily stored locally on a mobile device as an interface to the ultrasound device and manually copied from there to a local network drive of the University Hospital Dresden. The mobile devices are not connected to the Internet and are protected from unauthorized access by a password. Access to the network drive is only permitted to persons named in the ethics application. On the local drive, the patient age, patient gender and the diagnosis from the doctor's letter are then assigned to the images. Subsequently, this combined data set is anonymized and stored for evaluation. The test persons are assigned a number that does not allow any conclusions to be drawn about their identity and is only used for assignment within the anonymous data set.

Additional centers will record their data in the same form. Once anonymization and local storage have been completed, the data is manually inserted into the Dresden dataset via local data carriers.

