## 1. Summary

### Background

Ultrasound examinations have become an integral part of everyday clinical practice. Ultrasound imaging impresses with a combination of availability, freedom from radiation and high diagnostic gain. So far, however, it is above all the diagnostic gain that must be critically questioned, as ultrasound examinations are strongly dependent on the examiner. Especially for the evaluation of ultrasound images, a wealth of experience is necessary. A more objective evaluation is offered by the technique of quantitative ultrasound (QUS). A quantitative evaluation of so-called RF data (radiofrequency data) enables a more accurate diagnosis that is independent of the assessor. The gain in information is similar to the change from black-and-white television to color television. Physically, this is based on the individual, frequency-dependent sound reflection of tissues and pathologies depending on their biomechanical properties. This makes it possible, for example, to automate the segmentation of ultrasound images or the early detection of hepatic steatosis. Previous systems are based on narrowband piezo transducers, which is why a broadband analysis of tissue properties in the clinical setting has not yet been carried out. The approach is thus like promising ex-vivo studies, such as Gare et al., 2022, Nguyen et al., 2021 and Gangeh et al., 2014.

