## 2. Objective of the study

# Study protocol for the acquisition and frequency spectroscopic evaluation of broadband clinical

ultrasound raw data for tissue and pathology differentiation using neural networks

Department of Medicine I, University Hospital Carl Gustav Carus at TU Dresden

The aim of the study is to collect liver-specific ultrasound raw data and images, collect them in the form of a multicenter, anonymized, local database and subsequently evaluate them spectroscopically using methods like convolutional neural networks (CNN). The networks were trained on retrospective data from a separate ethics application (BO-EK-534122022) and are to be validated in these data primarily, but not exclusively. Should a sufficient amount of data arise to enable sufficient training, the use of the data for the training of the Networks would also be a goal.

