##### Risks

Due to the ultrasound systems used, no particular risks are to be expected. All devices used in the study are certified according to European safety standards for electrical equipment and approved for clinical use. The examinations carried out as part of the study are similar to normal clinical ultrasound examinations. Since these are carried out anyway, an additional

burden for the patients is inherently excluded. In addition, the ultrasound examination is considered non-ionizing and neither physically nor psychologically stressful. The total additional time required for the subject is approximately 5 minutes (2.5 minutes per ultrasound transducer).

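### Does building the broadband signal from two probes confound the bandwidth hypothesis (hypothesis 3)?

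*Protocol*

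**What the plan says.** Hypothesis 3 (Protocol, section 2, Initial more specific hypotheses) holds that the certainty with which an RF-trained network grades steatosis, fibrosis and cirrhosis "depends on the bandwidth of the US signal provided". It defines no bandwidth levels and names no comparison.

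Section 4, Course of study, names two handheld devices, one "used as a low-frequency abdominal transducer and Clarius' L15HD3 as a high-frequency linear transducer". On their joint use it says: "The data from the two transducers are combined in the evaluation to simulate broadband recordings". Raw data are kept only within a predefined region of interest; matching of that region between the probes is not described. Section 4, Risks, counts "2.5 minutes per ultrasound transducer", so the two recordings are separate scans.

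The motivation is in section 1. Background says "Previous systems are based on narrowband piezo transducers", and Goal says that "broadband raw ultrasound data are to be collected for the first time in a common database". Section 2 adds: "The networks were trained on retrospective data from a separate ethics application".

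**The concern.** Background describes earlier transducers as narrowband, and the composite is the only signal presented as broadband. A reader may conclude that one probe is the narrow level of hypothesis 3 and both probes together the broad level. In that contrast bandwidth does not vary alone: a second device is added, a second acquisition is added, and the tissue sampled may differ. Two readings of the same liver can classify better than one even when bandwidth plays no part.

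Broadband analysis is the study's declared novelty, so a gain from adding a probe that was reported as a gain from bandwidth would misstate a prominent result. A larger sample would not help, because the problem is one of attribution and not of precision.

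**Working it through.** The Protocol gives no AUC, error rate, power or effect size for hypothesis 3, so there is no figure of its own to reproduce. The check has two parts: how large the confounding could be if the one-probe versus composite contrast were used, and whether the text commits the study to that contrast.

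**Size, if that contrast were used**

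Assumptions, none from the Protocol: normally distributed scores, no bandwidth effect, first-probe AUC 0.80, 100 diseased and 100 not diseased (the Protocol targets at least 200 patients), a paired DeLong test at two-sided 5%, and AUC standing in for diagnostic certainty.

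- AUC = Φ(d/√2), so AUC 0.80 gives d1 = 1.190 and AUC 0.70 gives d = 0.742.
- Mean of two scores with correlation r: d = (d1 + d2)/√(2(1 + r)).

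With an equally good second probe, d1 + d2 = 2.380:

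| r | d of mean | AUC of mean | Significant gain, simulated (4000 trials) |
|---|---|---|---|
| 0.8 | 2.380/√3.6 = 1.254 | 0.81 | 20% |
| 0.5 | 2.380/√3 = 1.374 | 0.83 | 50% |
| 0 | 2.380/√2 = 1.683 | 0.88 | 95% |

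With the probe set and recordings held fixed and no true difference, the same test gives 2% to 3% in each direction. An upward artefact is therefore real under this contrast.

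A downward artefact is much less secure. Take a second probe with AUC 0.70 and r = 0.8.

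- Equal averaging: d = (1.190 + 0.742)/√3.6 = 1.018, AUC 0.764. This is an apparent loss, significant in 86% of simulated trials.
- Best linear weighting: d² = (d1² + d2² − 2r·d1·d2)/(1 − r²) = (1.416 + 0.551 − 1.413)/0.36 = 1.54, so d = 1.24 and AUC is about 0.81. There is no loss.

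The loss comes from forcing equal weights on two finished scores. The Protocol says that the transducers' data are combined, not that scores are averaged. A combination free to weight its inputs can give the weaker probe no weight, so apart from estimation error it need not fall below 0.80.

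**Does the text commit the study to that contrast?**

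- Hypothesis 3 speaks of the bandwidth of the signal supplied to a network. Varying the input bandwidth fits those words at least as well as switching probes.
- Background applies the term narrowband to earlier systems. It does not label either study probe as the narrow level.
- Course of study stores raw RF data from each probe, so each recording can be band-limited at analysis. Acquisition does not lock in the one-probe versus composite contrast.
- The same section says openly that the combination simulates a broadband recording. It does not claim a single wideband device.

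**What within-recording filtering would cost**

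It covers bandwidth only inside each probe's own range, which is a narrower question than the cross-probe idea. It may require retraining on the retrospective data, and the Protocol does not show that these contain suitable RF recordings. Power is limited. For a true rise from AUC 0.80 to 0.84 (assumed), simulation with 2000 trials gives:

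| Correlation between bandwidth levels | 100/100 split | 40/160 split |
|---|---|---|
| 0.9 | 75% | 57% |
| 0.8 | 49% | 36% |

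**The case for a change.** The strongest case for a change is that the Protocol itself fixes the composite beside a bandwidth hypothesis. The way the two recordings are taken, including whether both probes view the same tissue, cannot be repaired by an analysis plan once the data are in. One sentence defining the bandwidth levels would remove the risk at no burden to patients. A network that weights its inputs well would still benefit from a second reading, so the attribution problem in the upward direction remains.

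Much of this stands. A one-probe versus composite difference could not be credited to bandwidth alone, and weighting does not cure that. It is also true that matching of the region between probes is not described, although no mismatch is described either. What does not stand is the step to a fault in this document. Filtering each stored recording needs no match between probes, so a test free of the confounding stays available after collection. The missing sentence concerns how an analysis is set up, which a protocol commonly leaves to the analysis plan, and that plan is not at hand.

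**Conclusion.** No change follows. The confounding is conditional on a contrast that the Protocol does not adopt, and the data it collects leave another route open. What remains is an undefined analysis for one of six hypotheses that the Protocol itself calls initial. Evaluating the trained fibrosis network, and comparing RF-trained with B-scan-trained networks, do not depend on it.

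If the one-probe versus composite contrast were run, the plausible artefact is a gain: from an AUC of 0.80 to between 0.81 and 0.88 with an equally good second probe, depending on a correlation that the Protocol does not give. All inputs behind these figures are assumed. A loss is poorly supported, because it rests on equal averaging of finished scores.

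Choosing between cross-probe and within-recording bandwidth is a fair trade-off between a broader, confounded question and a cleaner, narrower one with modest power. An analyst setting up hypothesis 3 would in the ordinary course say how bandwidth levels are formed and describe any one-probe versus two-probe difference as the effect of adding a probe with its frequency band.

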## 6. Privacy

The procedure was coordinated with the data protection officer of the University Hospital (see DSB consultation result). No concerns were raised with regard to data protection.

Once enrolled in the study, subjects will receive a study participation ID that does not contain any personal identifying information. Since the subject's identity is no longer relevant to the study after the combination of ultrasound data and the clinical parameters such as age, gender and the diagnosis from the doctor's letter, the name of the subject is not noted in connection with the study ID or the data collected. Only the information sheets contain the names of the test subjects. These are only kept in paper form and stored in a lockable filing cabinet in the EKFZ together with other study-related forms.

All image data recorded during the study will be stored anonymously in local network servers of the University Hospital Dresden. The data collected during the study will be used exclusively for the purposes indicated and will not be shared with third parties. However, the local raw data will be stored for a maximum of ten years until the end of the evaluation, in accordance with the retention period specified by the German Research Foundation (DFG) or in accordance with the legally prescribed archiving period for clinical studies. After the end of the retention period, the files are deleted from all data carriers as well as data sheets (questionnaires, declarations of consent, etc.) are destroyed via the clinic's internal data protection-compliant document destruction.

All project staff and partners involved are subject to the European General Data Protection Regulation.

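### The reference test, its result and the fibrosis degree are not secured in the data set before it is anonymised without a key

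*Protocol*

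**What the plan says.** **Reference standards.** In section 2 of the protocol, hypothesis 1 is that network evaluation of the raw data "with liver elastography results as a reference standard enables the detection and classification of degrees of steatosis, fibrosis and cirrhosis". Hypothesis 4 makes the claim "with histology results as a reference standard enables the detection and classification of hepatic cavities". Hypothesis 5 has the same wording as hypothesis 4, with the CEUS result in place of histology.

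**Who enters.** Section 3 takes patients having biopsy, CEUS or elastography into one study. The Design part of the summary lets the ground truth follow each centre's local standard and lists CT and MRI as further examples.

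**What is attached.** Course of study (section 4) says that the raw data are recorded "shortly before the actual investigations, which provide us with the required ground truth". The labelling step then reads "the patient age, patient gender and the diagnosis from the doctor's letter are then assigned to the images". The next sentence is "Subsequently, this combined data set is anonymized and stored for evaluation". For other sites: "Additional centers will record their data in the same form", with anonymisation done locally before transfer to Dresden.

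**What link remains.** Section 6 refers to "the clinical parameters such as age, gender and the diagnosis from the doctor's letter" and states that "the name of the subject is not noted in connection with the study ID or the data collected". Names stand only on the paper information sheets.

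**What depends on the label.** Sample size planning (section 3) targets at least 200 patients. Once data collection is complete, it wants about 20 patients for each degree of fibrosis, failing which 100 more are recruited and the distribution is checked again. For focal lesions it plans 50 patients per lesion.

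**The concern.** The tests named as reference standards are not the item that the labelling step attaches. A diagnosis in a doctor's letter is a clinical conclusion. It may report the test result, but it may also draw on several sources, give no degree, or not say which test was used. No section requires the elastography result, the fibrosis or steatosis degree, the histology result, the CEUS result or the modality to be entered before the link to the patient is cut.

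Three things depend on this:

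- **Hypotheses 4 and 5** differ only in the reference test. Without the modality in the record they cannot be told apart.
- **Hypothesis 1** is a claim about agreement with elastography. With a label of unrecorded source, the evaluation may be measuring agreement with something else.
- **The recruitment rule** counts patients per fibrosis degree, so it needs a degree in every record and decides whether another 100 patients are enrolled.

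A statistical analysis plan can define how labels are used. It cannot restore a field that was never attached to a record that can no longer be traced to a patient. The count per degree is taken after data collection, so a missing degree would come to light when it could no longer be retrieved.

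**Working it through.** **Step 1: the sections side by side.**

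| Needed | Where it is needed | Secured before anonymisation? |
|---|---|---|
| Elastography result, steatosis and fibrosis degree | Hypothesis 1 | Not named; only if the letter gives it |
| Histology result | Hypothesis 4 | Not named; only if the letter gives it |
| CEUS result | Hypothesis 5 | Not named; only if the letter gives it |
| Modality that gave the label | To separate hypotheses 4 and 5 | Not named; only if the letter gives it |
| Fibrosis degree per patient | Count of about 20 per degree | Not named; only if the letter gives it |

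The order is label, then anonymise. Section 6 describes no key. Whatever is absent at the moment of anonymisation stays absent.

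**Step 2: focal lesions.** If no letter names the test, 0 of the 50 patients planned per lesion can be allocated to histology or to CEUS. If every letter names it, all can. The protocol does not say where between these ends the data will fall.

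**Step 3: fibrosis degree, illustration only.** The protocol gives no figure for label accuracy, so there is none to reproduce.

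*From the protocol:* 20 / 200 = 0.10, taken as the prevalence of the rarest degree.

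*Assumed:* five degrees, the other four at 0.90 / 4 = 0.225 each; letter label correct with probability Se = 0.95, 0.90 or 0.85 for every degree; true one-versus-rest AUC of 0.90 for the rare degree; errors spread equally over the other four degrees and independent of the network's score.

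*Formulas:*
- Sp = 1 − (1 − Se)/4
- PPV = 0.1·Se / [0.1·Se + 0.9·(1 − Sp)]
- NPV = 0.9·Sp / [0.9·Sp + 0.1·(1 − Se)]
- True cases among 20 labelled = 20·PPV
- Apparent AUC = 0.5 + (0.90 − 0.5)·(PPV + NPV − 1)

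| Se | Sp | PPV | NPV | True cases per 20 | Apparent AUC |
|---|---|---|---|---|---|
| 0.95 | 0.9875 | 0.095/0.10625 = 0.894 | 0.994 | 17.9 | 0.855 |
| 0.90 | 0.9750 | 0.090/0.11250 = 0.800 | 0.989 | 16.0 | 0.815 |
| 0.85 | 0.9625 | 0.085/0.11875 = 0.716 | 0.983 | 14.3 | 0.780 |

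**Step 4: sensitivity to the error pattern.** Suppose that errors fall only on neighbouring degrees: inner degrees split them in half, end degrees send all of them to their one neighbour. Suppose also that the network's score is ordinal: normal, unit variance, mean falling linearly with distance from the target degree, scaled to a true AUC of 0.90. The ranges run over whether the rare degree lies at an end, next to an end, or in the middle.

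| Se | True cases per 20 | Apparent AUC |
|---|---|---|
| 0.95 | 17.0–18.9 | 0.87–0.89 |
| 0.90 | 14.5–17.8 | 0.84–0.88 |
| 0.85 | 12.5–16.7 | 0.82–0.88 |

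The counts lie on both sides of those in step 3. The AUC loss is smaller, because the mislabelled patients resemble the target degree in score as well.

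**The case against.** The best case on the other side is that nothing here is contradicted, only left unsaid. Course of study opens by naming the investigations as the source of ground truth, so the letter diagnosis is plausibly the written outcome of the same examination. Section 6 gives its list as examples, so further fields are allowed. A label can be assigned only once a diagnosis exists, so the stated order already makes anonymisation wait for that diagnosis. A team that plans to count fibrosis degrees evidently expects each record to carry one. Records without a degree would simply not be counted, and recruitment would continue in blocks of 100. A field list agreed before the first anonymisation would close the gap.

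Much of this stands, and it rules out three stronger readings:

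- A reader might infer that the reference results will be lost, or that the protocol replaces them with the letter diagnosis. It does neither: the letter may carry test and result, and the list in section 6 is open.
- A reader might infer that records are anonymised before results arrive. No section says so.
- A reader might apply the independence formula of step 3 to neighbour-only errors and report an apparent AUC as low as 0.74 at 85% accuracy. That calculation lets labels stray only to neighbouring degrees, yet scores those neighbours like every other negative. It overstates the loss.

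What the objection does not do is secure anything. An intention stated in one sentence and an open list permit the reference result to be recorded; neither requires it. In particular, nothing secures the modality, which alone separates hypotheses 4 and 5. Nor is this a matter to leave to an analysis plan, because the protocol itself fixes when the link is cut.

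**Conclusion.** The concern holds as a gap in data capture: reference modality, result and degree are needed by hypotheses 1, 4 and 5 and by the recruitment rule, and no section makes their entry a condition of anonymisation. The loss is possible, not certain.

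Its size runs from zero, if the letters transcribe the test result and modality, to an inability to separate hypotheses 4 and 5 at all, if they do not name the test. For the fibrosis degrees, letter accuracy of 95, 90 or 85% would leave about 18, 16 or 14 true cases per 20 labelled and an apparent AUC of about 0.86, 0.82 or 0.78 with equally spread errors. With neighbour-only errors and an ordinal score the AUC would fall less. These figures rest on the assumed number of degrees, accuracies, true AUC and score models, and are not estimates for this trial. Extra recruitment caused by letters that state no degree is not included. The conclusion itself does not depend on these figures; it follows from the text.

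This should be fixed, because the loss would be irreversible for every record already anonymised, and the remedy is cheap.

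**What to change.** In Course of study and in section 6, require that every centre record the following before anonymisation:

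- the reference modality;
- its result or degree: elastography result with fibrosis and steatosis degree, histology result, or CEUS result.

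State that these recorded results are the reference for hypotheses 1, 4 and 5 and the basis for the count per fibrosis degree in Sample size planning. The letter diagnosis may stay as an additional field.

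The cost is transcription from examinations that are done in routine care anyway, a protocol amendment, and a check that the added fields do not weaken anonymity, which matters because a public database is planned. No new procedure is needed for patients. The change helps only records not yet anonymised, so it should be made before the first anonymisation or, failing that, as early as possible.
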